
Section 6
 
Purpose and rationale Insert purpose, objectives and research questions/hypotheses here.
	
The purpose of this study is 1) to test the feasibility and acceptability of an online program to improve the self-efficacy when completing complex care tasks among family caregivers to individuals living with mid-stage Alzheimer's Disease (AD), and 2) to evaluate whether participation in this program is likely to affect mean levels of self-efficacy and mastery.
 
Research Questions:
 
 1) Can Learning Skills Together be feasibly delivered to family caregivers to individuals living with mid-stage Alzheimer's Disease (AD) online, and is online delivery of Learning Skills Together acceptable to caregivers? 2) Do caregivers to individuals living with mid-stage AD have increased self-efficacy and mastery following completion of the Learning Skills Together program? 
Primary hypothesis: Caregivers to individuals living with mid-stage AD will have higher self-efficacy and mastery scores, on average, after completing the Learning Skills Together program.
 
Study aims:
 
Aim 1: Develop a manual to train interventionists to deliver a standardized version of LST. An interdisciplinary team of healthcare faculty with experience delivering an earlier version of the classroom-based intervention will prepare the content of this manual and its accompanying caregiver workbook.
 
Aim 2: Conduct a pilot study to test study protocols and examine outcome data to inform a sample size calculation for an efficacy study. We will implement LST in using videoconferencing over 2 weeks. Pre-post surveys examining self-efficacy and mastery will be administered to participants (N=40) to: 1) examine for trends for these outcomes, and 2) obtain effect size estimates to inform the sample size for a future study to test intervention efficacy. Analyses will be conducted using paired t-tests.
 
Aim 3: Examine the feasibility of delivering LST, intervention fidelity, and caregiver satisfaction. We will collect data on fidelity through direct observation by the interprofessional team on the delivery of their profession specific content using a structured fieldnote guide and fidelity checklist. Barriers and facilitators to delivering and participating in the program will be evaluated in post-session telephone debriefings with interventionists, as well as one-on-one in-depth interviews with 10 participants. To evaluate caregiver satisfaction, we will collect survey feedback data from caregivers after the workshop and booster session.
 
Given the circumstances surrounding COVID-19, while updating the Learning Skills Together program, we propose to test the feasibility of delivering LST online to adhere to social distancing recommendations.

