Study Setting and Recruitment. We will recruit a convenience sample of 40 caregivers. Caregivers learn about LST through word-of-mouth, community referrals, and local advertising (e.g., Eventbrite). We will cap classes at 12 caregivers per month, and deliver one course per month. As such, we anticipate recruiting ~6 caregivers/month for 8 months to meet our recruitment goal. (We will add sessions, if needed, to meet this recruitment goal.) When caregivers register for LST online or by phone, we will share information about the study with them (purpose, activities involved, risk and benefits) and screen for eligibility if they express interest in participating. Study information may also be shared through word-of-mouth referrals, community presentations, and flyers distributed by community partners and at events. We will aim to recruit 20 non-Latino and 20 Latino caregivers, such that participants represent the San Antonio community and the current clientele of the Caring for the Caregiver Program. **Regardless of whether a caregiver is interested in the research study and/or eligible to participate in the research study, they will still be allowed to participate in the Learning Skills Together program as it is being provided as a regular resource to the community.**

Inclusion and Exclusion Criteria. Inclusion criteria will follow those used by the National Institute on Aging-funded Resources for Enhancing Alzheimer's Caregiver Health (REACH) trials³⁵ such that: 1) the caregiver is a family member to an individual living with AD who has received a diagnosis from a physician, 2) they are aged 18 years or older, 3) they provide assistance with at least two instrumental activities of daily living or one activity of daily living, and 4) they are not paid to provide care. Further, participating caregivers must care for a person with living with moderate dementia, as measured by a score of 5 or 6 of the Global Dementia Scale.³⁶ We will also ask that participants be able to attend both the main workshop and the booster session. Exclusion criteria are: inability to read and speak English, and having plans to place the care recipient in a skilled nursing facility within the next 3 months.

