Intervention. Learning Skills Together is a 4-session online intervention delivered using the Zoom videoconferencing platform. Caregivers will be emailed call information, including a password, prior to the scheduled sessions, and will be asked to login at the scheduled time. Prior to joining the videoconference sessions, caregivers participating in LST will first meet with an interventionist during a one-on-one scheduled telephone call to 1) make sure the caregiver is prepared to participate (e.g., caregiver is comfortable with technology used to deliver LST), 2) build trust with the interventionist, and 3) set up individual goals. The 4 group-based Zoom-delivered sessions lasting ~1.5 hours each will cover topics including managing behavioral symptoms of dementia, communication, oral hygiene and other common complex care issues caregivers frequently encounter when assisting someone with mid-stage AD. Presentations will integrate discussion and interactive activities delivered using multiple web-based tools (e.g., videos, downloadable PDFs, chat box, polls). Presentations will be based on materials developed by an inter-disciplinary team of healthcare professionals and compiled into a caregiver workbook that will include standardized materials (e.g., Powerpoint slide decks, handouts). Zoom “breakout” groups will be used to facilitate small group discussion and activities. Additional resource and post-session assignments will be sent to participants by email. One month after completing the 4-week program, caregivers will participate in a booster session in which they will reflect on their goals and raise further questions they may have encountered since program completion.

Data Collection. Data will be collected using an online, self-administered questionnaire using REDCap. Surveys will be linked with a unique identifier. Outcomes will be measured at baseline (up to 2 weeks prior to workshop) (T₀), 1 month later (T₁), and 1 month after the booster session (T₂).

Table 2: Summary of pre- and post-test survey measures

Construct	Measure
Targeted proximal outcomes	
Self-efficacy (overall)	Pearlin and colleagues (1991) Competence Scale ($alpha=0.74$) ³⁷

Self-efficacy (responding to disruptive behaviors)	Revised Scale for Caregiver Self-Efficacy (test-retest reliability= r=0.70) ⁹

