Self-efficacy conducting complex care tasks (investigator-generated through expert discussion)	How confident caregivers feel conducting each task and skill area taught during the LST intervention (0=Not confident at all; 5=Very confident) ³
Caregiver Mastery	Pearlin and Schooler (1978) Mastery Scale (alpha -0.78) ³⁸
Participant characteristics	e.g., age, gender, race, ethnicity, relationship to care recipient, years in role
Caregiving intensity	Functional ability of the care recipient ^{39, 40} , presence of behavioral symptoms of dementia ⁴¹ , subjective stress ^{42, 43}

Sample size and justification. We will recruit 40 caregivers to account for attrition, such that we will have a final sample of 34 caregivers. We estimated this sample size using a power analysis conducted in G*Power where we assume a large effect size ($d=0.50$) with a 2-tailed test at 0.80 power with an alpha of 0.05. The effect size, which may be arguably sizeable, is traditional for a pilot study; these data will inform subsequent power calculations in a future large-scale trial. ⁴⁴.

Aim 3: We propose multiple methods to examine the delivery feasibility, fidelity, and caregiver satisfaction.

Examining interventionists' fidelity to the training manual through direct observation. *Data Collection.* Each member of the interdisciplinary team responsible for developing the training manual will observe at least one workshop to examine how the section(s) they developed is(are) being implemented. Feedback will be recorded in a structured field-note worksheet as well as a checklist of essential components for delivery ⁴⁶. Checklists will be developed collaboratively while developing the training manual. A second observer will also observe each session to monitor fidelity. *Analysis:* Checklist scores from each observer will be summed at each session; we will calculate a kappa score to examine inter-rater reliability. Qualitative notes will be reviewed, and a content analysis will be applied to identify additional measures of fidelity and to refine existing items.

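### Does the observer rule leave too few paired ratings for the planned fidelity kappa?

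*Combined protocol and SAP*

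**What the plan says.** The fidelity component is in Section 9.1, Aim 3. Two rules decide who observes what. Each member of the interdisciplinary team "will observe at least one workshop to examine how the section(s) they developed is(are) being implemented". Then: "A second observer will also observe each session to monitor fidelity". Section 6, Aim 3 describes the team's part as "direct observation by the interprofessional team on the delivery of their profession specific content using a structured fieldnote guide and fidelity checklist", so an expert rates their own content.

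The analysis is one sentence: "Checklist scores from each observer will be summed at each session; we will calculate a kappa score to examine inter-rater reliability". It gives no unit for the kappa, number of doubly rated sessions, target value or precision. Section 9.2 does not mention the kappa under Aim 3.

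The instrument is not final: "Checklists will be developed collaboratively while developing the training manual". Section 9.1, Aim 1 adds that a fidelity checklist is already in use and will be revised for this programme. Refinement of the items is assigned to content analysis of the qualitative notes, not to the kappa.

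The volume of delivery comes from the recruitment and intervention paragraphs of Section 9.1: "We will cap classes at 12 caregivers per month, and deliver one course per month"; "we anticipate recruiting ~6 caregivers/month for 8 months to meet our recruitment goal"; and "Learning Skills Together is a 4-session online intervention delivered using the Zoom videoconferencing platform".

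**The concern.** A kappa needs two observers' marks on the same item in the same session. The second observer is placed at each session, but the only number attached to the expert is a minimum of one workshop, for that expert's own section(s). A pair exists only where the two rules meet, so the plan guarantees one pair per item even though the course runs about eight times.

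Summing scores by session makes matters look worse. Section 7 lists five professions for the earlier version of the programme. If all five kept a section across four sessions, at least one session would hold two professions' content. There the expert's sum and the second observer's sum would cover different items, and could differ even with perfect agreement.

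At stake is the only stated reliability figure for the fidelity checklist. If it cannot tell careful observation from careless, the fidelity scores in the pilot report rest on less than they appear to. Paired observations also cannot be added once the courses have finished.

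**Working it through.** The plan states no number of pairs, target kappa or precision, so there is no figure to reproduce. The check counts the pairs and then asks what a kappa from them could show.

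**1. Pairs from the documents**

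- Deliveries: 8 months × 1 course = 8 courses; 8 × 4 = 32 core sessions.
- If classes fill: 40 / 12 = 3.3, so 4 courses.
- Literal minimum, assuming one developer per section: 1 pair per item, which is 1/8 = 12.5% of deliveries, or 1/4 = 25% if 4 courses suffice.
- If two members developed a section, each owes an observation and the minimum is 2.
- If two observers rate every session: about 8 pairs per item and 32 paired session sums.

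**2. What each unit of analysis gives at the minimum**

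- *Per item, n = 1.* Kappa is 0/0 if the observers agree and 0 if they disagree. It carries no information.
- *Session sums, n at most 4.* Treating the sum as a binary rating for illustration, the formula in step 3 gives a half-width of 1.33 at kappa 0.6 and prevalence 0.9. This is of no use.
- *Items pooled over sessions, n = number of items.* This is the usual way to calculate agreement on a checklist, and steps 3 and 4 use it.

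**3. Large-sample precision of the pooled kappa**

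For two raters with equal marginals and a binary item with prevalence p:

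Var(κ) = (1/n)(1 − κ)[(1 − κ)(1 − 2κ) + κ(2 − κ) / (2p(1 − p))]

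With κ = 0.6 and p = 0.9 (both assumed): 0.4 × [0.4 × (−0.2) + 0.84/0.18] = 1.835, so the 95% half-width is 1.96 × √(1.835/n). With κ = 0.8 and p = 0.8: 0.2 × [0.2 × (−0.6) + 0.96/0.32] = 0.576.

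| Jointly rated items (n) | κ 0.6, p 0.9 | κ 0.8, p 0.8 |
|---|---|---|
| 20 | 0.59 | 0.33 |
| 40 | 0.42 | 0.24 |
| 80 | 0.30 | 0.17 |
| 160 (e.g. 20 items × 8 courses) | 0.21 | 0.12 |

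Items within a session are correlated and the experts differ, so true precision is somewhat worse.

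**4. Can it separate better from worse observation?**

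Assumed, because the documents do not give them: yes/no items, delivery probability beta(17,3) by session (mean 85%), and independent mis-marking of 5% or 10% per observer.

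Expected values at 5%:
- Agreement = 0.95² + 0.05² = 0.905.
- Share marked delivered = 0.85 × 0.95 + 0.15 × 0.05 = 0.815.
- Chance agreement = 0.815² + 0.185² = 0.698.
- Kappa = (0.905 − 0.698)/(1 − 0.698) = 0.69 (0.685 unrounded).

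At 10%, agreement is 0.9² + 0.1² = 0.82, the share marked is 0.78, chance agreement is 0.78² + 0.22² = 0.657, and kappa is 0.48.

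Simulated pooled kappa with one doubly observed workshop:

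| Items | Mean kappa, 5% mis-marking | 95% range | Worse pair (10%) scores at least as high: kappa | Same, percent agreement |
|---|---|---|---|---|
| 20 | 0.64 | −0.05 to 1.00 | 29% | 29% |
| 40 | 0.66 | 0.26 to 0.94 | 21% | 17% |
| 80 | 0.67 | 0.38 to 0.87 | 12% | 7% |

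Repeat runs put the 40-item lower limit between 0.23 and 0.27. The last column is exact binomial: the sum over x of P(X₁₀ = x) × P(X₅ ≤ x), with X₁₀ ~ Bin(n, 0.82) and X₅ ~ Bin(n, 0.905).

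**5. What the alternatives would buy**

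- *More double observation.* With 40 items and four workshops the range is 0.51 to 0.82 and mis-ranking falls to 3.5%. One workshop is 4 × 1.5 = 6 hours of delivery and four are 24 hours, shared among the experts.
- *Percent agreement in place of kappa.* From the table, no gain at 20 items, 4 points at 40 and 5 points at 80. It drops the chance correction where chance alone gives about 70% agreement.
- *Naming the unit and the number of paired sessions.* This adds no data.

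**The case for a change.** The strongest case for acting is that the count comes from the protocol's own words and the remedy is a sentence. Fidelity is a named part of Aim 3, kappa is its only reliability figure, and Section 9.2 omits it. The unit is open between items and session sums, and two of the possible units fail outright at the guaranteed minimum. The number of paired sessions must also be fixed before delivery ends.

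Much of this stands: the minimum is one pair per item, the unit is not stated, and a short checklist would give a wide range.

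The conclusion that the kappa is uninformative does not stand. A second observer at each session, with scores from each observer summed at each session, can be read as two raters throughout. The documents do not exclude that reading, and the one workshop is expressly a minimum. On the pooled item reading, the better pair scores higher in about 79% of cases at 40 items (100% − 21%), which is imprecise rather than empty. The size of the problem also depends on a checklist length and error rates that the documents do not contain. The mismatch of session sums needs all five professions to keep a section, and Section 7's list describes the earlier programme.

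**Conclusion.** No change follows. The plan leaves the unit of the kappa and the number of doubly rated sessions open. An analyst will fill that gap sensibly once the checklist exists, by comparing item-level marks on items both observers rated, giving the number of such items, and keeping session sums as description. Requiring more double observation would be a staffing choice: a single-site pilot may fairly spend expert time elsewhere. Replacing kappa with percent agreement is a matter of preference, with a gain of 0 to 5 percentage points in the comparison above.

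The size is bounded. At the literal minimum with 40 items, the pooled kappa ranges from about 0.26 to 0.94; with pairs from four workshops it ranges from 0.51 to 0.82. These figures rest on assumed yes/no items, 85% delivery and 5% mis-marking, and on one developer per section. No threshold or go/no-go rule uses the kappa, field notes and debriefings also inform delivery, and the Aim 2 analyses and the sample size of 40 are untouched. A kappa from few paired sessions should simply be read as imprecise.

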9.1 Step-by-Step Methods

Provide a comprehensive narrative describing the research methods.

Aim 1: The interdisciplinary team of healthcare faculty who have delivered the Caregiving Skills intervention over the previous 3 years will build on their existing materials and experiences to develop a standardized LST training manual during the first two months of the pilot study year. In addition to updating existing presentations and learning objectives, faculty and topics experts will integrate interactive activities and handouts for family caregivers. Team members will provide guidance for a general audience, so that the program can be administered by interventionists with a variety of qualifications in different settings. After drafting sections, the investigator team and Caregiver Specialist, a former caregiver, will review and suggest revisions. The draft training manual and workbook will then be shared with the whole team for a second review round. Adherence to manual procedures will be examined as a part of intervention fidelity in Aim 3. We currently use a checklist to examine fidelity in the skills workshop, and this will be revised for LST.

Aim 2: Using a pre-post design, caregivers will complete self-administered surveys up to 2 weeks prior to participating in the LST program, 4 weeks later, and 4 weeks after the booster session that will occur 6 weeks after the final core LST group session. Data will be used to examine trends and to obtain effect size estimates to calculate the sample size for a future efficacy study.

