We will compare scores on self-efficacy and mastery at T_0 , T_1 , and T_2 . We will first examine bar graphs for caregivers in aggregate and for each caregiver; the x-axis will be the assessment number (i.e., T_0 , T_1 , T_2) and the y-axis will be the targeted outcome scores. Next, we will compare the means and dispersion at each assessment point for each score. Finally, we will conduct t-test analyses to detect statistically significant differences in mean scores over time. *Exploratory analyses.* We will also complete exploratory analyses on stratified samples to assess differences in scores according to caregiver ethnicity and caregiving intensity. Although the sample size will likely be too small to observe differences, we may observe informative trends. Finally, we will compare the characteristics of participants who completed the intervention and those who dropped out to inform retention efforts in future studies.

Aim 3:

Discussion notes, transcribed interviews, and reflection worksheets will be analyzed with thematic content analysis, a method we selected for its flexibility⁴⁷. Data will be iteratively coded by two members of the research team with input among the investigative team.

4. Lorig K. Chronic disease self-management. *American Behavioral Scientist.* 2016;39:676-683

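### Does the fidelity kappa need a stated unit and weighting, given that the checklist scores are summed for each session?

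*Combined protocol and SAP*

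**What the plan says.** Section 6 plans fidelity data by direct observation, "using a structured fieldnote guide and fidelity checklist". Section 9.1, Aim 1, links this to the manual: "Adherence to manual procedures will be examined as a part of intervention fidelity in Aim 3".

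The detail is in section 9.1, Aim 3. The instrument is "a checklist of essential components for delivery", and it is not yet final: "Checklists will be developed collaboratively while developing the training manual". Each content developer observes at least one workshop, looking at the section or sections that he or she wrote. In addition, "A second observer will also observe each session to monitor fidelity".

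The reliability analysis is one sentence: "Checklist scores from each observer will be summed at each session; we will calculate a kappa score to examine inter-rater reliability". The next sentence deals with the qualitative notes, to which "a content analysis will be applied to identify additional measures of fidelity and to refine existing items".

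Section 9.2 does not mention the checklist under Aim 3. Its text there starts "Discussion notes, transcribed interviews, and reflection worksheets will be analyzed with thematic content analysis" and stays with the qualitative material.

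**The concern.** The only quantity named before the kappa is the session sum, so a reader may take it that kappa is computed on the sums. Two difficulties would follow.

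- A total discards which items were marked. Two observers can reach the same total from different omissions, and no statistic on totals can detect that. For a checklist of essential components, agreement on the components is the more informative question.
- A total is an ordered score with many levels. Unweighted kappa treats a one-point gap as complete disagreement, so it can look poor when the observers agree on nearly every item.

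This is the only inter-rater check planned for the checklist, and the plan gives no unit, weighting or pooling rule. Two analysts could therefore report different statistics from the same records. At stake is the Aim 3 estimate of fidelity reliability.

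**Working it through.** **Inputs.** The documents give no kappa value, target, item count, response format or number of double-rated sessions, so there is no planned figure to reproduce. About 32 core sessions can be derived from section 9.1 (about 8 monthly courses x 4 sessions). That is an upper case, because developers need attend only one workshop. Everything else below is an assumption, shown over a range.

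**1. What totals can hide.** Suppose both observers score 15 of 20 yes/no items, with k omissions in common.

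- Item agreement = (10 + 2k)/20
- Chance agreement = 0.75² + 0.25² = 0.625
- Item kappa = (agreement - 0.625)/0.375

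| Shared omissions k | 0 | 1 | 2 | 3 | 4 | 5 |
|---|---|---|---|---|---|---|
| Item agreement | 0.50 | 0.60 | 0.70 | 0.80 | 0.90 | 1.00 |
| Item kappa | -0.33 | -0.07 | 0.20 | 0.47 | 0.73 | 1.00 |

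The totals are equal in every column, so the property is real.

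**2. How often it would occur.** Let each observer err independently on an item with probability e. The two disagree on an item with probability q = 2e(1 - e), and either direction is equally likely. With n items:

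- P(no item disagreement) = (1 - q)^n
- P(equal totals) = sum over j of C(n,2j) q^(2j) (1 - q)^(n-2j) C(2j,j)/4^j
- P(equal totals that hide a disagreement) = the second minus the first

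For n = 20 and e = 0.10, q = 0.18. Equal totals occur with probability 0.214 and no disagreement with probability 0.82^20 = 0.019. The difference is 0.195 of all sessions, which is 91% of the sessions with equal totals.

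| Items | Rater error | Equal totals | Hidden, share of all sessions | Hidden, share of equal-total sessions |
|---|---|---|---|---|
| 5 | 2% | 83% | 1% | 1% |
| 5 | 5% | 64% | 3% | 5% |
| 5 | 10% | 46% | 9% | 20% |
| 10 | 2% | 70% | 3% | 4% |
| 10 | 5% | 46% | 9% | 20% |
| 10 | 10% | 31% | 18% | 56% |
| 20 | 2% | 52% | 7% | 14% |
| 20 | 5% | 31% | 17% | 56% |
| 20 | 10% | 21% | 20% | 91% |

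The last column looks alarming only because its denominator shrinks. Where totals differ, the reader already sees that some disagreement exists, though not on which items.

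**3. Effect of unit and weighting.** Simulated means for 32 sessions, 10 yes/no items, 85% delivered and 5% rater error were: item kappa 0.68, unweighted kappa on totals 0.32, quadratic-weighted kappa on totals 0.79. The choice can therefore move the reported number. For yes/no items the weighting question disappears, because weighted and unweighted kappa coincide.

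**4. Which reading the text supports.** The semicolon joins two statements, that scores are summed and that a kappa is calculated. Neither says that the second uses the first. Kappa is a statistic for categorical ratings, and a checklist of components supplies these item by item. The observer arrangement points the same way. A developer who rates only his or her own section would have a sum over fewer items than the observer who follows the whole session. Such sums would not be comparable, whereas the items that both rated would be.

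**5. What depends on it.** No kappa threshold or decision rule is set. Item refinement is tied to the content analysis of the notes, not to the kappa. The Aim 2 outcomes and the sample size of 40 do not involve it.

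**The case for a change.** The strongest case for a change is that the gap is plain and cheap to close. Nothing in the document supplies the unit, and section 9.2 does not repeat the fidelity analysis. If only totals were kept, item agreement could not be recovered later. As the checklist was still to be built, a sentence would have secured the item ratings at almost no cost.

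Much of this stands. The unit and weighting are indeed unstated, the choice affects the number reported, and a clarifying sentence would do no harm. Three points weigh against treating it as a fault in the plan.

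- A checklist is completed item by item, so its records hold the item ratings unless someone discards them. The plan nowhere says that they will be discarded.
- Weighting cannot sensibly be fixed before it is known whether items are yes/no or graded.
- The silence of section 9.2 means little here, since the satisfaction-survey analysis for Aim 3 also appears only in section 9.1.

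Item kappa has a weakness of its own, because it falls when nearly everything is delivered. In simulation with 10 items and 5% rater error, it averaged 0.76, 0.68 and 0.60 at 75%, 85% and 90% delivered, while raw agreement stayed at 0.90 to 0.91. Percent agreement would need to stand beside it, which is again a matter of ordinary reporting.

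**Conclusion.** No change to the plan is needed. The text leaves the unit of the kappa open; it does not specify a wrong one. An analyst with the finished checklist would naturally compute agreement on the items that both observers rated and report the summed score separately.

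Even if totals were used, matching totals would conceal an item disagreement in about 1% to 20% of all sessions. That range assumes 5 to 20 yes/no items, independent rater errors of 2% to 10%, and both observers rating every item; the documents give none of these values. The consequence is confined to one descriptive reliability estimate in a feasibility pilot, with no threshold or decision attached and no bearing on Aim 2. A report of the results should state which unit and weighting were used.

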Post-workshop telephone debriefings to examine barriers and facilitators to intervention delivery per interventionists. *Data collection:* After completion of each LST monthly program, we will conduct a telephone debriefing session with interventionists and students to discuss strengths and weaknesses in program delivery and ways to improve its administration. **One-on-one interviews to examine barriers and facilitators to delivery per caregivers, as well as application of training.** *Data collection:* In-depth semi-structured one-on-one half-hour interviews will be conducted with 10 participants. Caregivers will be asked about their experiences, including what they learned, barriers to participation, and changes they recommend, including how to improve LST's cultural relevance and tailoring to individual needs. *Recruitment.* We will circulate flyers at the workshop to recruit caregivers. Participant will be compensated \$20 for their time. **Reflective journals to evaluate caregiver learning and application of skills.** We will also collect caregivers' reflective journal entries to assess caregiver learning from all participants. Entries will be from worksheets completed for the booster session. *Analysis:* Discussion notes, transcribed interviews, and reflection worksheets will be analyzed with thematic content analysis, a method we selected for its flexibility ⁴⁷. Data will be iteratively coded by two members of the research team with input among the investigative team.

Self-administered surveys to assess caregiver satisfaction with LST. *Data.* All caregivers who participate in the LST intervention will receive a satisfaction survey immediately following the workshop and after the reflective booster sessions. Surveys will be completed online or by phone. Surveys will ask about satisfaction with each program component and the program's structure. *Analysis:* Descriptive statistics will be used to examine satisfaction survey data, including means, frequencies, and measures of dispersion.

9.2 Data Analysis Plan *Provide the plan for data analysis (include as applicable the sample size calculation).*

Aim 1:

Not applicable

Aim 2:

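### Interviewees are asked how to improve LST's cultural relevance, but the 10 are recruited by flyer alone and the 20/20 Latino and non-Latino enrolment aim is not carried over to them

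*Combined protocol and SAP*

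**What the plan says.** All of this is in section 9.1 of the combined protocol and SAP.

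- **Interviews (Aim 3).** "In-depth semi-structured one-on-one half-hour interviews will be conducted with 10 participants". Their stated purpose is to learn what helps or hinders delivery from the caregiver's side and how the training is applied. Caregivers are asked about their experiences, including what they learned, obstacles to taking part, and "changes they recommend, including how to improve LST's cultural relevance and tailoring to individual needs".
- **Interview recruitment (Aim 3).** "We will circulate flyers at the workshop to recruit caregivers", with $20 for taking part. No quota, purposive sampling, ethnicity criterion or rule for choosing among responders is given here or in section 9.2.
- **Enrolment (Aim 2, Study Setting and Recruitment).** "We will recruit a convenience sample of 40 caregivers", and "We will aim to recruit 20 non-Latino and 20 Latino caregivers", so that participants reflect the San Antonio community and the programme's clientele. Caregivers who decline or do not qualify for the study are not turned away: "they will still be allowed to participate in the Learning Skills Together program".
- **Other caregiver feedback (Aim 3).** Reflective worksheets come from all participants and assess learning and use of skills. Satisfaction surveys cover the programme's components and structure. Neither is described as covering cultural relevance.
- **Ethnicity in the analysis (section 9.2).** It appears only in exploratory stratified analyses of scores.

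**The concern.** The plan cares about ethnic balance when it enrols and about cultural fit when it interviews, but does not connect the two. Section 7 says half of the more than 250 caregivers reached by the earlier programme were Latino, and that content was adapted to be more culturally familiar to them. The interviews are the only component described as asking about cultural relevance, yet who is interviewed depends on who responds to a flyer.

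At stake is how much weight the cultural-relevance recommendations can bear. If 3 or fewer of the 10 interviewees come from one group, what that group would change rests on very few voices. No other planned source is described as filling the gap, and a sampling rule cannot be added once the interviews are done.

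**Working it through.** **The plan's own figure.** The documents give no calculation for the 10 interviews. The one sample-size figure is for the paired t-test: d = 0.50, "with a 2-tailed test at 0.80 power with an alpha of 0.05", "such that we will have a final sample of 34 caregivers". Exact noncentral-t power is 0.808 at n = 34 and 0.795 at n = 33, so 34 is the smallest adequate number. With 15% loss (1 − 34/40), 34/0.85 = 40. The figure reproduces, and nothing below changes it.

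**Inputs for the interviews.** 10 interviews (Aim 3), and a pool of 20 Latino and 20 non-Latino caregivers (the Aim 2 enrolment aim, taken as met exactly). The response odds of the two groups are not in the documents and are varied below.

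**Equal volunteering.** Let X be the number of Latino caregivers among the 10. Then X is hypergeometric:

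P(X = k) = C(20, k) × C(20, 10 − k) / C(40, 10), with C(40, 10) = 847,660,528.

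- k = 0: 184,756
- k = 1: 20 × 167,960 = 3,359,200
- k = 2: 190 × 125,970 = 23,934,300
- k = 3: 1,140 × 77,520 = 88,372,800

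Cumulating from k = 0:

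- P(X ≤ 1) = 3,543,956 / 847,660,528 = 0.004
- P(X ≤ 2) = 27,478,256 / 847,660,528 = 0.032
- P(X ≤ 3) = 115,851,056 / 847,660,528 = 0.137

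The expected number is 10 × 20/40 = 5. By symmetry, the chance that one or other group supplies 3 or fewer is 2 × 0.1367 = 0.273. With the pool reduced to 17 and 17 after attrition, P(X ≤ 2) is 0.029 and P(X ≤ 3) is 0.129, so the answer hardly moves.

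**Unequal volunteering (assumed odds).** The ranges span the Fisher and Wallenius noncentral hypergeometric distributions, pool 20 and 20.

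| Latino response odds relative to non-Latino | Mean Latino interviewees | P(1 or fewer) | P(2 or fewer) | P(3 or fewer) |
|---|---|---|---|---|
| 1 | 5.0 | 0.004 | 0.03 | 0.14 |
| 3/4 | 4.4–4.5 | 0.01 | 0.07–0.08 | 0.25–0.26 |
| 1/2 | 3.5–3.7 | 0.04–0.06 | 0.19–0.22 | 0.45–0.50 |
| 1/3 | 2.8–3.0 | 0.12–0.16 | 0.37–0.44 | 0.67–0.73 |
| 1/4 | 2.3–2.5 | 0.21–0.27 | 0.51–0.60 | 0.79–0.85 |

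If the odds ran the other way, at 2, P(2 or fewer Latino) would be about 0.002, and by symmetry the 1/2 row would describe the non-Latino group.

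**Effect of a minimum.** If at least 4 of the 10 come from each group, the split can be no worse than 6 to 4. With flyers alone and equal volunteering, that happens with probability 1 − 0.273 = 0.727.

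**The case against.** The case for leaving the plan alone has several sound parts.

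- **Purpose of the interviews.** A reader might infer that the interviews exist to settle cultural relevance. They do not. It is one item under recommended changes, paired with individual tailoring, and it is not named in the research questions or the aims of section 6. This stands and limits the weight of the point.
- **Near absence.** A reader might infer that Latino caregivers are likely to be almost missing. With equal volunteering that is improbable (0.004 for 1 or fewer). It becomes material only if Latino response is markedly lower, and nothing in the documents suggests so; the history of half-Latino attendance points, if anything, the other way. This stands.
- **Comparing groups.** A reader might infer that a between-group comparison of themes would be lost. None is planned: section 9 describes one thematic content analysis, and about five half-hour interviews per group would support a contrast only weakly. This stands.
- **The selection rule and the pool.** The text does not say how 10 are chosen if more respond, so a first-come rule is an inference. The 20/20 split is an aim within a convenience sample, and the workshop is open to caregivers outside the study, so a pool of exactly 20 and 20 is a modelling assumption. This stands, but it cuts both ways: the pool reached by flyer may be less balanced than modelled.
- **Other feedback.** Worksheets and satisfaction surveys reach far more caregivers than the interviews. As described, they do not ask about cultural relevance, so they soften the gap without closing it.

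What remains is that the plan seeks advice on cultural relevance, names flyers alone as the route to interviewees, and leaves their ethnic mix to chance.

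**Conclusion.** The point holds as a minor, inexpensive improvement to the qualitative part of Aim 3. Even with no difference in willingness to be interviewed, there is roughly a one-in-four chance (0.27) that one group supplies 3 or fewer of the 10. That figure assumes a pool of exactly 20 and 20. The higher risks for Latino caregivers specifically, such as 0.19 to 0.22 for 2 or fewer at half the response odds, rest on an assumption the documents neither support nor exclude. The primary hypothesis, the Aim 2 estimates, the sample size of 34 from 40 and the t-tests are untouched.

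**What to change.** In the interview Recruitment text of section 9.1, Aim 3, keep the flyers and add a minimum per group: for example, at least 4 of the 10 interviews from Latino and at least 4 from non-Latino caregivers. Where flyer responses fall short, reach the minimum by inviting enrolled participants directly, using the ethnicity recorded at baseline (T0; ethnicity is listed in Table 2). Do this as classes proceed, so that interviews stay close to the workshop. Report the interviewees' ethnic mix beside the cultural-relevance themes. A fixed 5/5 split, places held back until the last class, and reporting themes by group are not needed.

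The cost is a sentence or two in the protocol, a few extra invitations and possibly slower filling of the last places. The number of interviews and the $20 payment do not change.
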